10.3 Severity of Adverse Events and Serious Adverse Events

The severity of each AE or SAE must be assessed by the Investigator or designee.

- Mild: The AE is transient or causes mild discomfort. There usually is no intervention/therapy required and the AE does not interfere with the participant's normal activities.
- Moderate: The AE causes some limitation in activity and some assistance may be needed. Treatment for the AE may be needed.
- Severe: The AE causes marked limitation in activity. The participant's usual daily activity is interrupted. The participant may require medical intervention/therapy; hospitalization is possible.

10.4 Outcome of Adverse Events and Serious Adverse Events

The outcome of each AE and SAE must be noted in the source documents and CRF.

- Not recovered / not resolved – the event has not improved
- Recovered / resolved – the participant has recuperated from the event
- Recovered / resolved with sequelae – the participant has recuperated from the event but retained pathological conditions resulting from the event
- Recovering / resolving – event is improving

- Unknown – either not known, not observed, not recorded, or participant refused to provide information
- Fatal – death as a result of the AE

10.5 Assessment of Relatedness to Study Product

The Investigator or designee will assess each AE and SAE for causality based on their best medical judgement, the observed symptoms associated with the event, and the available information on the investigational product.

- Not Related: No evidence of any causal relationship with the investigational device or trial intervention.
- Possibly Related: Some evidence to suggest a causal relationship between the AE and the investigational device or trial intervention, but other factors may have contributed to the event.
- Probably Related: Evidence suggests a causal relationship with the investigational device or trial intervention; the influence of other factors is unlikely.
- Definitely Related: Evidence suggests a causal relationship to the investigational device or trial intervention, i.e., follows a known or suspected pattern of response, or is otherwise logically related to the investigational device or trial intervention, and no alternative cause is present.

10.6 Reporting Serious Adverse Events

Prompt notification of the Sponsor regarding SAEs is essential so that regulatory responsibilities and legal obligations can be satisfied. The Investigator must report SAEs according to the following time frames.

- Initial notification of all SAEs based on the available information must be provided to the Sponsor or designee by phone within 24 hours of the investigational site learning of the event. Initial notification within 24 hours of death or life-threatening events is extremely important.
- Follow-up information, when available, must be sent to the Sponsor or designee within 48 hours of receipt of the information by the investigational site

The Investigator must comply with all applicable local regulatory requirements related to reporting SAEs to the IRB.

The Investigator should institute appropriate therapeutic and follow-up measures in accordance with good medical practice and should notify the monitor of such actions and record them in the participant's CRF.

10.6.1 *Serious Adverse Event Information to Report*

At a minimum, SAE reports must contain the participant ID number, the serious adverse event term, onset date, relationship to study product, and a brief description of the event. Causality should be included in the initial report.

11 POTENTIAL ANTICIPATED ADVERSE EVENTS

The following potential anticipated AEs are transient and may be associated with use of the VCool Intranasal Cooling System:

- Nosebleed
- Shivering
- Irritation of the nasal passages
- Skin irritation at the site of the cannula
- Nasal congestion

11.1 Immediate Post-Procedure Observations

There are observations that are expected events immediately post-procedure that would be expected with any procedure. Any event that does not require medical management will not be considered significant but will be documented and reported.

11.2 Unanticipated Adverse Device Effect

An Unanticipated Adverse Device Effect (UADE) is any serious adverse effect on health or safety or any life-threatening problem or death caused by, or associated with use of the VCool device, if that effect, problem, or death is not identified in nature, severity, or degree of incidence in this Investigational Plan (protocol) or any other unanticipated serious problem associated with the VCool device that relates to the rights, safety, or welfare of the participants participating in this study.

11.3 Reporting

All AEs, UADEs, and SAEs will be reported via the CRFs. All AEs meeting the above definitions of an UADE and/or SAE, whether device-related or not, must also be reported to the study Sponsor within 24 hours of discovery and to the approving IRB as soon as possible, based on IRB requirements but in no event later than 10 working days after the Investigator first learns of the AE or effect.

12 DATA ANALYSIS

12.1 Primary Analysis

The time and flow rate that is required to reduce and maintain each participant's core temperature to 35.5°C from measured baseline temperature will be calculated. The total number of participants who reach the target temperature in 2 hours or less will be calculated.

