5 STUDY ENDPOINTS

5.1 Primary Endpoints

1. To confirm the VCool System can lower core body temperature to 35.5°C within 2 hours.
2. To identify whether cooling with the VCool System results in a gradient between brain and core body temperature.
3. To confirm the VCool System can maintain a core body temperature between 35°C and 36°C for one hour after cooling.

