2. If temperature continues to fall below 35°C after 2 minutes, cover patient with electric blanket that has been pre heated on standby. Keep blanket on until temperature gets back to 35°C.

Assess for shivering every 10 minutes using the BSAS. Record the results and time. The BSAS is recorded throughout the study.

Bedside Shivering Assessment Scale

0	None
1	Mild: Shivering localized to neck/thorax
2	Moderate: Intermittent involvement of the upper extremities and/or thorax
3	Severe: Generalized shivering or sustained upper and/or lower extremity shivering

The flow can be increased to 40 liters per minute after 10 minutes

Record any VCool System adjustments to flow rate or temperature and record the new flow rate and temperature and time of adjustment. Record the reason for the adjustment.

Assess the participant for adverse events (AEs) throughout the study

If the participant has a nosebleed, discontinue the study and note the time.

Monitor patient at first sign of shivering

- If **Mild**, cover patient with regular blanket.
- If **Moderate or severe** – discontinue cooling treatment.

Continue to record the temperature until either temperature sensor reaches 35.5°C or the VCool System has been used for 2 hours. Note the time the target temperature was achieved.

If the participant's core body temperature does not reach 35.5°C in 2 hours, the study is concluded

- Remove the nasal cannula from the participant and dispose of it properly
- Monitor the participant's core body temperature until it returns to baseline. Blankets can be applied to help with warming.
- Remove the axillary thermometer

If the participant's core body temperature reaches 35.5°C, proceed to the next steps

Maintain the target temperature of 35.0°C to 36.0°C for 1 hour:

Adjust flow rate by 5 liters per minute from baseline every 2 minutes

- If temperature falls below 35°C., reduce flow rate by 5 liters per minute every 2 minutes until temperature rises back to 35°C
- If temperature rises above 36°C, increase flowrate 5 liters per minute every 2 minutes until temp falls below 36°C

Remove the nasal cannula and the air delivery tube and dispose of them properly

Once out of the MRI suite, record the patient temperature (°C) using the 3M SpotOn® zero-heat-flux forehead sensor, the Braun ThermoScan 7 tympanic sensor

Monitor the participant's core body temperature until it returns to baseline. Blankets can be applied to help with warming.

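### The maintenance primary endpoint (35 to 36°C held for one hour) has no matching result in the primary analysis, which names 35.5°C and counts only participants reaching target

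*Protocol*

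**What the plan says.** Section 5.1 of the protocol lists three primary endpoints. Two concern core temperature alone:

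- Induction: "To confirm the VCool System can lower core body temperature to 35.5°C within 2 hours".
- Maintenance: "To confirm the VCool System can maintain a core body temperature between 35°C and 36°C for one hour after cooling". This is item 3 in section 5.1 and item 2 in the synopsis.

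The objective in section 2.2 uses the same band and hour. So does the procedure in section 7.6.3: "Maintain the target temperature of 35.0°C to 36.0°C for 1 hour".

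Section 12.1, Primary Analysis, has two sentences. One calculates the time and flow rate needed to lower and then hold each person's "core temperature to 35.5°C from measured baseline temperature". Its other sentence is the count: "The total number of participants who reach the target temperature in 2 hours or less will be calculated". Section 12.2 covers shivering and adverse events, 12.3 the study population and 12.4 the imaging data.

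**The concern.** Four places in the protocol describe maintenance as a band held for an hour. The section that says what will be calculated replaces the band with a single value, omits the hour, and counts only those who reach target. If section 12.1 is followed as written, the study report will show how many participants were cooled and at what settings. It will not show how many stayed between 35 and 36°C for one hour. An endpoint worded as something to confirm would then have no figure to confirm or refute it, and a reader could take the induction count as evidence for both endpoints.

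**Working it through.** The protocol states no power, significance level, success threshold or derived sample size, so there is no planned figure to reproduce. The check sets the text side by side and then shows by arithmetic what the stated count leaves open.

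**1. Endpoint against analysis**

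| Source | Temperature | Duration | Result produced |
|---|---|---|---|
| Synopsis; 5.1; 2.2; 7.6.3 | 35 to 36°C | one hour | (definition of the aim) |
| 12.1, first sentence | 35.5°C | none given | time and flow rate per participant |
| 12.1, second sentence | target temperature | reached in 2 hours or less | number of participants |
| 12.2, 12.3, 12.4 | none for core-temperature maintenance | none | shivering and adverse events; population; imaging |

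No row of the analysis section gives a number, proportion or time in band for the maintenance hour.

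**2. What the section 12.1 count leaves open**

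Let k of the 10 participants reach target and m of those k hold the band for one hour. The protocol reports k. The endpoint asks about m, and k restricts it only to 0 ≤ m ≤ k.

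Illustration with an assumed k = 8 (the protocol gives no expected count), using exact Clopper-Pearson 95% intervals:

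| Quantity | Result | 95% CI |
|---|---|---|
| Reach target (what 12.1 reports) | 8/10 | 44.4% to 97.5% |
| Hold band, if m = 0 | 0/10 | 0% to 30.8% |
| Hold band, if m = 4 | 4/10 | 12.2% to 73.8% |
| Hold band, if m = 8 | 8/10 | 44.4% to 97.5% |

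Among the 8 who reached target, the same three cases are 0/8 (0% to 36.9%), 4/8 (15.7% to 84.3%) and 8/8 (63.1% to 100%). The one reported count fits all of them.

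**3. Can the missing result be derived from the data collected?**

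Section 7.6.3 has core temperature recorded every 2 minutes. A full hour gives 60/2 + 1 = 31 readings, counting both ends, which is enough for an in-band summary.

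Whether a full hour is observed is less clear. The synopsis gives an additional hour after target, and section 7.6.3 also has one hour. Section 4.1 monitors until two hours are completed. If those two hours run from the start of cooling, which is the natural reading, a participant reaching target at minute t has 120 − t minutes left:

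- t = 60: 60 minutes
- t = 90: 30 minutes
- t = 120: 0 minutes

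On that reading, anyone reaching target after minute 60 has less than one observed hour. Section 4.1 also says the participant comes off VCool once the study endpoint is reached, yet has the device's ability to maintain temperature assessed afterwards. It is therefore unclear which readings reflect the device in use.

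**The case against.** The strongest reply is that this is a single-arm feasibility study in 10 people with no hypothesis test. On that view section 12.1 merely compresses the objective in section 2.2, the readings are taken anyway, and a separate analysis plan may supply the detail. Part of this stands. Section 12.1 does mention maintaining temperature, so it would be wrong to say that it has no maintenance output at all. No error rate is at stake. Intervals and the handling of brief excursions can properly be left to an analysis plan. But the protocol states a primary analysis, and that text names a different target from its own endpoint. A plan that followed section 12.1 would carry the mismatch forward, and one that followed section 5.1 would contradict section 12.1.

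Three stronger readings are tempting, and the document does not support them:

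- A reader might infer that a participant steady at 35.9°C meets section 5.1 but fails section 12.1. Section 12.1 sets no pass/fail rule for maintenance, so there is nothing there to fail.
- A reader might infer from the two directional bullets in section 7.6.3 that flow changes only once temperature has left the band, so that every participant needing control has already failed. The line above those bullets, "Adjust flow rate by 5 liters per minute from baseline every 2 minutes", carries no out-of-band condition. Section 5.1 also does not say that one stray reading is failure.
- A reader might infer that readings under the electric blanket would be credited to the device. Section 7.6.3 uses the blanket only below 35°C and until 35°C is regained, so those readings lie almost entirely outside the band. What remains is that the blanket step is silent on reapplying the cannula.

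**Conclusion.** The concern holds as a contradiction in the protocol's stated text: the maintenance primary endpoint is a band held for one hour, and no stated analysis yields a result for it. The count in section 12.1 is compatible with anything from none to all of those who reach target holding the band. The effect is an unreported or ambiguously reported primary endpoint. It does not bias the induction result or affect any error rate. The conclusion rests on the wording of sections 5.1, 7.6.3 and 12.1 to 12.4 alone; the assumed 8 of 10 only illustrates it. The readings needed are already planned, provided the maintenance hour is actually observed, and section 4.1 leaves that in doubt.

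**What to change.** Amend section 12.1 to report, besides the number reaching 35.5°C within 2 hours:

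1. The number and percent, with exact 95% CI, of all participants starting cooling who reach target and then stay within 35.0 to 36.0°C for 60 minutes. Those who never reach target stay in the denominator.
2. The percent of the two-minute readings in that hour that lie in the band.
3. A statement that only readings taken with VCool in use count as maintained by VCool.

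The time and flow-rate description can remain, with its maintenance part worded to match the band and hour in section 5.1. A second version that tolerates brief excursions is optional.

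Before this, reconcile section 4.1 (monitoring until two hours are completed, and removal from VCool at the endpoint) with the synopsis and section 7.6.3 (a further hour of maintenance), so that the one-hour result can be observed for everyone who reaches target. Rewording section 12.1 alone cannot supply an hour that was not observed.

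Cost: a text amendment and one extra table from readings already planned. The maintenance figure may look less favourable than the induction count.

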12.2 Secondary Analysis

The incidence of any shivering will be analyzed using the BSAS. The incidence and nature of any adverse events or participant intolerance will be tabulated.

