5.2 Secondary Endpoint

4. To assess the shivering experienced by participants based on the 4-point Bedside Shivering Assessment Scale (BSAS).

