7.6 Procedure

7.6.1 **VCool System Set Up**

Attach the disposable delivery tube to the VCool System

Install the gas inlet filter on the back with the filter bowl vertical (glass side down)

Attach the air hose to the gas inlet filter

Connect the power cord to a grounded outlet

Turn the power switch to "ON"

Connect the RS232 cable to the VCool System and to the laptop computer

Turn on the computer

Select the following:

TC-48-20 program.

COM5

Communications

Set Point and set value to -19.0

Controller options

Save data to file

Go to file Explorer, select LabView Data

Select New and enter participant identification number as file name

Save data to file

Turn on gas and set flow meter to 35 liters per minute.

Confirm temperature is set to -10°C

Confirm gas temperature setting at the end of the delivery tube is -5°C

Attach nasal cannula to the delivery tube

7.6.2 *MR Imaging procedure*

- Participants will undergo MRI at the HSF3 research facility at the University of Maryland, Baltimore (UIMB). Each imaging session will last approximately 90 minutes. The protocol will include high-resolution anatomical MRI for structural reference and tissue segmentation; MR Spectroscopy (MRS) to measure metabolite and water resonance frequencies for temperature estimation; MR Thermometry to measure phase changes over time to track temperature dynamics; Perfusion MRI to measure cerebral blood flow (CBF); as well as other structural and functional imaging sequences. These sequences will be repeated at multiple time points during the controlled cooling period to monitor temporal changes in temperature, perfusion, and tissue properties.

7.6.3 *Participant Set Up and Monitoring*

Have the participant lie on their back in an inclined position and place the nasal cannula on the participant, securing the straps around their head

Record the temperature from both temperature sensors and record the time

Record the flow rate

Initiate the cooling and record the time. The induction phase for participant cooling can take up to 2 hours.

Record the core body temperature every 2 minutes from both temperature sensors and record the time. The core body temperature is monitored throughout the study.

If the core body temperature is <35°C for 5 minutes:

1. Remove nasal cannula, if temperature starts to rise after 2 minutes keep cannula off until temperature gets back to 35°C. Then reapply nasal cannula and resume treatment.

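### Section 12.2 summarises shivering as an incidence with no link to temperature reached or cooling time, so few shiverers cannot be told apart from participants who never got cold

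*Protocol*

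**What the plan says.** Section 5.2 makes shivering on the 4-point Bedside Shivering Assessment Scale (BSAS) the only secondary endpoint. Section 12.2 states its analysis: "The incidence of any shivering will be analyzed using the BSAS". The same section also tabulates adverse events and participant intolerance. Section 12.1 reports, separately, each participant's time and flow rate to target and the number who reach target within 2 hours.

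Section 7.6.3 sets how long each participant is cooled and what is recorded:

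- Target missed: "If the participant's core body temperature does not reach 35.5°C in 2 hours, the study is concluded".
- Target reached: "Maintain the target temperature of 35.0°C to 36.0°C for 1 hour".
- Mild shivering leads to a blanket. For moderate or severe shivering the instruction is to "discontinue cooling treatment". A nosebleed also ends the session.
- Shivering: "Assess for shivering every 10 minutes using the BSAS", then "Record the results and time. The BSAS is recorded throughout the study".
- Temperature: "Record the core body temperature every 2 minutes from both temperature sensors and record the time".

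Two of these rules are contradicted elsewhere. Section 2.3.2 has flow and temperature adjusted, not stopped, for severe shivering. Section 4.1 ends monitoring at two hours in total, whereas Section 7.6.3 and the synopsis add an hour after target.

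**The concern.** Whether someone shivers depends on how cold they become and for how long. In this design both depend on how well the device cools. A participant whose temperature hardly moves is watched for at most 2 hours with little reason to shiver. A participant who cools well is colder and is watched for longer. An incidence that ignores temperature and time counts a non-shiverer of the first kind the same as one who stayed comfortable at 35.5°C.

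The rationale in Section 2.4 describes existing methods as poorly tolerated by awake patients and expects this device to do better. Shivering is the protocol's main measure of that expectation. If the summary cannot separate tolerated cooling from absent cooling, it does not inform the expectation, and a weak device would show the more favourable figure.

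**Working it through.** The protocol states no expected shivering rate and no target for this endpoint, so there is no figure to reproduce. Steps 1 and 2 use only the protocol. Steps 3 and 4 rest on assumed rates and show direction and rough size only.

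**1. Exposure and depth that the rules allow**

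- Fall needed to reach 35.5°C from the eligible baseline in Section 6.1: 36.8 − 35.5 = 1.3°C, up to 37.5 − 35.5 = 2.0°C.
- Target missed: at most 120 min, so 120/10 = 12 BSAS readings. The fall may be anything short of target, including almost none.
- Target reached (Section 7.6.3): up to 120 + 60 = 180 min, so up to 180/10 = 18 readings, the last hour at 35 to 36°C. Under Section 4.1 the limit would be 120 min.
- Stopped early (nosebleed, or moderate or severe shivering): possibly minutes.

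**2. Can the planned data link shivering to depth?** Yes. BSAS is timed every 10 minutes and temperature every 2 minutes, so each BSAS reading has a temperature beside it.

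**3. Size of the depth effect (assumed model)**

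Let the shivering rate be k × (fall − 0.5°C) once the fall exceeds 0.5°C, with linear cooling and k from 0.3 to 1.0 per °C-hour. Then P(any shivering) = 1 − exp(−k × A), where A is the area of the fall above 0.5°C in °C-hours.

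| Course | A | P at k = 0.3 | P at k = 1.0 |
|---|---|---|---|
| 0.3°C lost over 2 h | 0 | 0% | 0% |
| 0.7°C lost over 2 h | ½ × 0.571 × 0.2 = 0.057 | 2% | 6% |
| 1.5°C lost over 1 h, held 1 h | ½ × 0.667 × 1.0 + 1.0 = 1.333 | 33% | 74% |
| 1.5°C lost over 2 h, held 1 h | ½ × 1.333 × 1.0 + 1.0 = 1.667 | 39% | 81% |

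Among 10 participants this is about 0 to 0.6 expected shiverers in the first two rows and 3.3 to 8.1 in the last two, with the same tendency to shiver. The second and third rows both last 2 hours, so dividing by hours of cooling would not remove the difference. Temperature has to enter the summary.

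Even 0 of 10 leaves an exact 95% upper limit of 1 − 0.025^(1/10) = 31%, before asking how cold the ten became.

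**4. Does the stop for shivering lower the incidence?** No. Anyone stopped for grade 2 or 3 has already shivered and is already counted. A simulation agrees. It assumed onset at 0.25 per hour, progression at 0.5 per hour, 30% starting at moderate, severe reached only through moderate, and a 3-hour session. Any shivering was 53.0% and moderate or worse 35.5%, with and without the stop. The stop removed later progression to severe (16.4% without it, 0 with it) and cut mean exposure from 3.0 to 2.5 hours.

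**The case against.** The strongest objection is that Section 12.2 is a one-sentence summary and the detail may sit in a statistical analysis plan that is not shown. The data are secured, and this is a single-arm study of 10 people with no test or tolerability threshold. Section 12.1 reports the number reaching target, so a device that fails to cool will be seen to fail. Section 12.2 also tabulates intolerance, and Section 8 requires the reason for any discontinuation to be recorded.

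Much of this stands, and it keeps the point small. It does not remove it. The protocol is not silent: it names the measure, and that measure has no temperature or time in it. The count reaching target stands apart from the shivering result and does not show who shivered, or at what temperature.

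Three stronger readings are tempting, and the protocol does not support them:

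- *Stopping for shivering biases the incidence down.* It does not, as step 4 shows, and mild shivering does not stop cooling at all.
- *Mild shivering is pooled with moderate and severe.* The word any suggests it, but analysis using the BSAS can equally mean incidence by grade.
- *Participants stopped for shivering drop out of the denominator.* Section 7.3.1 screens until 10 have completed and Section 12.3 describes 10 volunteers. Neither says whether a stopped participant counts as a completer. If such people were replaced and left out, the incidence would be too low, but the protocol does not say that they are.

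**Conclusion.** The point holds as a minor weakness of interpretation. The stated summary cannot separate tolerance at 35.5°C from never getting cold, and nothing else in the protocol's analysis section makes that link. That exposure and depth differ follows from the protocol's own rules: up to 2 hours against up to 3 hours under Section 7.6.3, and a fall from almost nothing to 1.3 to 2.0°C at target. How much they will differ in practice is unknown.

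The illustrated contrast of 2 to 6% against 39 to 81% depends on the assumed 0.5°C threshold, the assumed rates and linear cooling, and is not a forecast. The direction needs only that shivering becomes more likely with deeper cooling. If Section 4.1's two-hour limit applies, the difference in maximum duration disappears, but the difference in depth remains.

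**What to change.** In Section 12.2, replace the single incidence with one listing that covers every participant who started cooling:

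- worst BSAS grade (0, 1, 2 or 3);
- elapsed cooling time and core temperature at the first grade 1 or higher, and at the first grade 2 or higher;
- total cooling duration and lowest core temperature.

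Beneath it, show the distribution of worst grade split by whether 35.5°C was reached. Name the sensor that supplies the temperature, since Section 7.6.3 records two. The incidence of any shivering can stay as one line of this table.

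The contradictions that affect exposure must also be reconciled: Section 2.3.2 against Section 7.6.3 on the response to severe shivering, and Section 4.1 against Section 7.6.3 on the length of monitoring after target. Which rule applies is for the sponsor and the investigator to settle.

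The shivering change needs wording only. BSAS, temperature and their times are already collected, so the cost is a longer table of about 10 rows.
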